### 9.2 Determination of Sample Size

The proportion ( $\hat{p}$ ) of mild/moderate bleeding episodes treated with each dose of LR769 that are classified as being successfully treated will be compared with an objective performance criterion (OPC) of 0.55. A one-sided, one-sample normal approximation test, with an alpha = 0.0125 (adjusted from 0.025 to 0.0125 to account for multiplicity of testing), will be used to test the null hypothesis that  $p \leq 0.55$  versus the alternative hypothesis that  $p > 0.55$ , where  $p$  is the true proportion of mild/moderate bleeding episodes that are classified as successes. (Note: The standard error used in the denominator of the test statistic will account for the correlation among bleeding episodes for a given patient.) This will be done for each treatment regimen.

With the assumptions of a true proportion of success of 0.70, a correlation among bleeding episodes for a given patient of 0.1, and an OPC of 0.55, a sample size of 22 patients with a total of 352 mild/moderate bleeding episodes (assuming 8 bleeding episodes per treatment regimen per patient) will provide statistical power  $\geq 80\%$ . The study will enroll at least 24 patients, in order to account for dropouts and potential unevaluable bleeding episodes.

### 9.3 Analysis Populations

The Enrolled Population will be defined as all patients who signed informed consent. Analyses of non TEAEs will be done on the Enrolled Population.

The Safety Population will be defined as all patients who received treatment (either in Phase A and/or Phase B). All analyses of safety will be performed based on the Safety Population.

The Treated Population will be defined as all patients who received treatment for at least one bleeding episode, and each such bleeding episode will be analyzed as treated. All analyses of efficacy will be performed based on the Treated Population.

The Evaluable PK Population will be defined as all treated patients who have a post-study drug administration factor VIIa activity level. All PK analyses will be based on the Evaluable PK Population.

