### **3 INVESTIGATIONAL PLAN**

#### **3.1 Overall Study Design and Plan**

[figure not shown]
This is a global, multicenter, Phase III, prospective, open-label, randomized, crossover study. There are two patient age ranges (birth to < 6 years and  $\geq$  6 years to < 12 years); 12 patients will be enrolled within each age range.

After obtaining informed consent (from parents/guardians and assent of the patient if applicable) and performance of screening procedures, patients who meet all inclusion and exclusion criteria will be randomized to start with one of the two treatment regimens:

- 75  $\mu$ g/kg treatment regimen
- 225  $\mu$ g/kg treatment regimen

The assigned treatment regimen is the dose administered in the safety phase, Phase A, for the initial assessment of safety and PK, and the dose to be used when starting the treatment phase, Phase B, before crossover to the other treatment regimen (Figure 1).

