## **5.9 Packaging and Labeling**

The investigational product, LR769, will be supplied in clear glass vials as lyophilized powder of 1 mg and 5 mg. The vials will be labeled using multilingual labels, which will comply with local regulations and requirements. Vials will be packaged in an outer box. In addition, prefilled syringes with Water for Injection, as well as supplies for reconstitution and administration of the study drug will be provided.

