The null hypothesis will be tested using a one-sided, one-sample, normal approximation test and a test statistic obtained by dividing ( $\hat{p} - 0.55$ ) by its estimated standard error, taking into account the correlation between bleeding episodes for a given patient. The test will be conducted at the 0.0125 level (adjusted from 0.025 to 0.0125 to account for multiplicity of testing). Treatment of mild/moderate bleeding episodes in the study with LR769 of a given dose will be regarded as successful if it is concluded that the true percentage of successfully treated bleeding episodes with that dose is greater than 0.55. The primary endpoint for the FDA is to satisfy the requirements of the US FDA for the evaluation of success.

No imputation of missing data will be performed for the primary analysis of the primary efficacy endpoint. However, two sensitivity analyses will be performed in order to examine the effect of missing data, if any, on the results of the primary analysis. In the first sensitivity analysis, all bleeding episodes for which the value of the primary efficacy endpoint is missing will be assigned as failures. In the second sensitivity analysis, all such bleeding episodes will be assigned as successes.

In addition, the proportions of successfully treated mild/moderate bleeding episodes will be compared between the two LR769 treatment doses at a 2-sided alpha of 0.05.

Two sensitivity analyses based on Generalized estimating equations (GEE) logistic regression analyses and Generalized linear mixed effects models (GLMM) will be used to assess the robustness of the result by accounting for the within-subjects correlation.

The primary efficacy endpoint for the EMA is defined as the proportion of bleeding episodes (mild/moderate and severe combined) with a “good” or “excellent” patient (for mild/moderate bleeding episodes) and physician (for severe bleeding episodes) reported assessment of efficacy at 12 hours after the first administration of study drug. This proportion of success will be evaluated by the EMA as part of the assessment of the benefit risk ratio for each dosing regimen.

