3. SHELL TABLES FOR THE NEW ANALYSES

Table Addendum 14.2.8.1.1 Number of Administrations of Study Drug and Time Required to Reach a Response (FDA Definition) - Mild/Moderate Bleeding Episodes (Treated Population)

Parameter	Statistic	75 µg/kg (N=xx)	225 µg/kg (N=xx)	Overall (N=xx)
Number of administrations of study drug required to produce a response (BEs with response only)	n	xx	xx	xx
	nmiss	xx	xx	xx
	Mean (SD)	xx (xx.x)	xx (xx.x)	xx (xx.x)
	Median	xx	xx	xx
	Q1/Q3 Minimum/Maximum	xx.x/xx.x xx/xx	xx.x/xx.x xx/xx	xx.x/xx.x xx/xx
Time required to reach a response (hours) (BEs with response only)	n	xx	xx	xx
	nmiss	xx	xx	xx
	Mean (SD)	xx (xx.x)	xx (xx.x)	xx (xx.x)
	Median	xx	xx	xx
	Q1/Q3 Minimum/Maximum	xx.x/xx.x xx/xx	xx.x/xx.x xx/xx	xx.x/xx.x xx/xx
Kaplan-Meier Model results for Time required to reach a response (hours) (All BEs) Censored Summary	Bleeding Episodes with Event	xx (xx.x%)	xx (xx.x%)	xx (xx.x%)
	Censored Bleeding Episodes	xx (xx.x%)	xx (xx.x%)	xx (xx.x%)
	Missing	xx (xx.x%)	xx (xx.x%)	xx (xx.x%)
	Kaplan-Meier Estimates			
	Q1 (C.I.)	xx.x (xx.x, xx.x)	xx.x (xx.x, xx.x)	xx.x (xx.x, xx.x)
	Median (C.I.)	xx.x (xx.x, xx.x)	xx.x (xx.x, xx.x)	xx.x (xx.x, xx.x)
	Q3 (C.I.)	xx.x (xx.x, xx.x)	xx.x (xx.x, xx.x)	xx.x (xx.x, xx.x)

Note: Table is stratified by actual treatment regimen at bleeding episode.

Table Addendum 14.2.8.1.2 Number of Administrations of Study Drug and Time Required to Reach a Response (FDA Definition) - Mild/Moderate Bleeding Episodes (Treated Population) - Patients from birth to less than 2 years

Similar to Table Addendum 14.2.8.1.1

Table Addendum 14.2.8.1.3 Number of Administrations of Study Drug and Time Required to Reach a Response (FDA Definition) - Mild/Moderate Bleeding Episodes (Treated Population) - Patients 2 years to less than 6 years

Similar to previous

Table Addendum 14.2.8.1.4 Number of Administrations of Study Drug and Time Required to Reach a Response (FDA Definition) - Mild/Moderate Bleeding Episodes (Treated Population) - Patients 6 years to less than 12 years

Similar to Table Addendum 14.2.8.1.1

Table Addendum 14.2.8.2.1 Number of Administrations of Study Drug and Time Required to Reach a Response (EMA Definition) - Bleeding Episodes Regardless of Severity (Treated Population)

Similar to Table Addendum 14.2.8.1.1

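### The between-dose comparison, the one efficacy contrast that relies on the randomised crossover, classifies bleeds by the regimen given, and the documents supplied show no analysis by assigned regimen

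*Protocol*

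**What the plan says.** Protocol section 9.3 defines the Treated Population as patients treated for at least one bleed and states that "each such bleeding episode will be analyzed as treated". The scope is general: "All analyses of efficacy will be performed based on the Treated Population". The synopsis repeats both statements.

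Section 9.5.1 first sets out the one-sample test of each dose against the objective performance criterion (OPC) of 0.55. It then adds that the success proportions in mild/moderate bleeds "will be compared between the two LR769 treatment doses at a 2-sided alpha of 0.05". No separate attribution rule is given for this comparison. The sensitivity analyses in 9.5.1 deal with missing outcomes and within-patient correlation, not with regimen attribution. Section 3 of the SAP addendum uses the same approach in a new descriptive table produced after database lock: "Table is stratified by actual treatment regimen at bleeding episode".

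On the design, section 3.1 says: "This is a global, multicenter, Phase III, prospective, open-label, randomized, crossover study". Section 7.2.1.2 fixes the dose for a bleed by the patient's randomisation and current 12-week period. After Phase A, families may hold drug at home for mild/moderate bleeds (6.6). It is "supplied in clear glass vials as lyophilized powder of 1 mg and 5 mg" (5.9), with no mention of regimen-specific vials. Doses given at home are recorded in a diary (5.8).

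**The concern.** The tests against 0.55 do not depend on randomisation. The comparison of the two doses does: the randomised sequence and the fixed 12-week periods are what make bleeds under one regimen comparable with bleeds under the other. As-treated classification lets something that happens after randomisation, namely the dose actually drawn up, decide the column in which a bleed is counted.

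If a family departs from the scheduled regimen because a bleed looks easy or hard, that bleed takes its prognosis into the other column. The contrast then partly reflects the difficulty of the bleeds. An apparent dose difference could arise where none exists, or a real one could be distorted, and no analysis in the supplied documents would show it.

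**Working it through.** **The plan's own figure.** Inputs from section 9.2: true success 0.70, OPC 0.55, within-patient correlation 0.1, 22 patients, 8 bleeds per regimen per patient, one-sided alpha 0.0125.

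- Bleeds per regimen: 22 × 8 = 176; total 352.
- Design effect: 1 + (8 − 1) × 0.1 = 1.7.
- SE at 0.70: √(0.70 × 0.30 × 1.7 / 176) = 0.0450. SE at 0.55: √(0.55 × 0.45 × 1.7 / 176) = 0.0489.
- Power: 81.5% with the null variance in the critical value, 86.2% with the alternative variance. Both agree with the stated 80% or more.

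**Effect of as-treated classification on the between-dose contrast.** Assume no true dose difference, with success p = 0.70 on both regimens. Let a fraction f of bleeds in 225 µg/kg periods receive the 75 µg/kg regimen, and let those bleeds have success s. With 176 bleeds scheduled per regimen:

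- 75 µg/kg column: (p + fs) / (1 + f)
- 225 µg/kg column: (p − fs) / (1 − f)
- False difference: 2f(s − p) / (1 − f²)

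The documents give neither f nor s; both are assumptions. With s = 0.90:

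| f | Bleeds moved | 75 column | 225 column | False difference |
|---|---|---|---|---|
| 2% | 3.5 | 70.4% | 69.6% | 0.8 points |
| 5% | 8.8 | 71.0% | 68.9% | 2.0 points |
| 10% | 17.6 | 71.8% | 67.8% | 4.0 points |

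For f = 5%: (123.2 + 7.92) / 184.8 = 0.7095 and (123.2 − 7.92) / 167.2 = 0.6895.

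The mirror case, in which harder bleeds with 50% success in 75 µg/kg periods receive the 225 µg/kg regimen, gives the same sizes and again favours 75 µg/kg. If s = 0.70, so that the departure is unrelated to the bleed, the false difference is 0 at any f. Classified by assigned regimen, it is 0 in every row.

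**Against sampling error.** The SE of the difference is √(2 × 0.21 × (1.7/8 − 0.1) / 22) = 0.0463 if patient effects cancel in the crossover, or √2 × 0.0450 = 0.0637 if the regimens are treated as independent. The actual error of the two-sided 0.05 test (crossover SE; independent SE) is then:

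- f = 2%: 0.053; 0.052
- f = 5%: 0.072; 0.061
- f = 10%: 0.141; 0.097

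**The case against.** Several points stand on the other side.

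- **No choice of dose.** A reader might infer that families select the regimen bleed by bleed. The documents do not support that: section 7.2.1.2 fixes the regimen. The mechanism is deviation or error, and it biases a null contrast only if it depends on the bleed.
- **Controls exist.** Staff compare diary entries with remaining vials (5.8), used vials are brought back (5.11), contact is about weekly (7.3), eCRF data are fully source-verified with diaries among the sources (10.6), and important deviations are analysed in the study report (10.9). These make a high rate of selective departures less likely. They do not change how a discordant bleed is classified.
- **Secondary role.** Section 9.2 sizes the study on the tests against 0.55, and section 9.5.1 judges each dose on that test. The between-dose comparison is additional.
- **Main SAP not seen.** The SAP addendum refers to main SAP version 2.0, which may contain an analysis by assigned regimen. Its absence can be asserted only for the documents supplied. The shell-table note belongs to a descriptive table and does not itself govern the between-dose test.
- **As-treated does not make the OPC proportions immune.** In the 5% example they become 71.0% and 68.9%. It remains a reasonable main classification there, because the question is how each regimen performed when given.
- **By-assigned analysis has a cost.** If a true difference d exists and a fraction f of one regimen's bleeds receive the other, the by-assigned contrast becomes about d(1 − f), provided d is the same in those bleeds. At f = 5% an assumed 10-point difference would appear as 9.5 points.

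**Conclusion.** The point holds in a limited form. Section 9.3 applies as-treated classification to the one efficacy contrast that relies on the randomised sequence, and the supplied documents offer no analysis by assigned regimen beside it.

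The size is unknown because no rate of wrong-regimen bleeds is given. With 70% success on both regimens and 90% in the bleeds that cross, the false difference is 2.0 points at 5% and 4.0 points at 10%. It is small at 2% or less, and zero if departures are unrelated to the bleed and the doses are equally effective.

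Two stronger readings are tempting and should not be drawn. One is that the between-dose result will be biased: nothing in the documents shows that bleed-dependent departures occur at any material rate. The other is that the trial's main conclusions on each dose are undermined: those rest on the tests against 0.55, for which as-treated can stay. The change is worth making because it is cheap and alters nothing if no bleed is discordant.

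**What to change.** In protocol sections 9.3 and 9.5.1 and in the SAP:

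1. Make the between-dose comparison, and any GEE or GLMM model that estimates the dose contrast, by assigned regimen. Take this from the randomisation schedule and the patient's actual crossover dates at bleed onset. The derivation must handle the ±5-day window of the crossover visit (7.3.3) and any 12-week period paused for surgery and resumed (3.1.2.5).
2. Keep as-treated as a sensitivity analysis for that comparison, and as the main analysis for the tests against 0.55 and for safety.
3. Tabulate the bleeds where assigned and actual regimen differ, by period and direction.
4. Define actual regimen for analysis purposes. The 225 µg/kg regimen may continue with 75 µg/kg doses (3.1.2.2), so individual doses do not identify it.

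The cost is a wording change, one derived variable and one table, with no new data collection. The statistical price is slight dilution of the by-assigned contrast if a true dose difference exists and departures occur. If main SAP version 2.0 already contains this analysis, only section 9.3 and its cross-references need aligning.

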## 9.4 Demographics and Baseline Characteristics

Demographic and baseline characteristics for all patients, patients in the PK group and for patients in each dose group will be summarized using descriptive statistics for continuous variables and frequencies and percentages for categorical variables.

## 9.5 Primary Endpoint

### 9.5.1 Primary Efficacy Endpoint

The primary efficacy endpoint for this study is defined as successful treatment of a bleeding episode at 12 hours after first administration of the study drug. The following are clarification definitions to satisfy regulatory requirements in multiple regions (i.e., the FDA and the EMA).

For primary efficacy endpoint for the FDA, only mild/moderate bleeding episodes are taken into account. Severe bleeding episodes will be a minority of the bleeding episodes treated in the study, and require further treatment even if the bleeding has improved. Efficacy in severe bleeding episodes will be analyzed separately, using descriptive statistics only.

The primary efficacy endpoint for the FDA is defined as the successful treatment of a bleeding episode at 12 hours (bleeding episode level), where a success is defined as meeting all of the following criteria:

- *Good or Excellent* response noted by patient/parent/guardian, depending on patient's age and maturity
- Study drug treatment: No further treatment with study drug beyond timepoint where a Good or Excellent response for this bleeding episode was noted
- No other hemostatic treatment needed for this bleeding episode
- No administration of blood products indicating continuation of bleeding beyond timepoint where a Good or Excellent response for this bleeding episode was noted
- No increase of pain beyond timepoint where a Good or Excellent response for this bleeding episode was noted that cannot be explained other than as continuation of bleeding

For each LR769 treatment, the proportion ( $\hat{p}$ ) of mild/moderate bleeding episodes rated as successfully treated at 12 hours will be summarized using the count and percentage. A 95%

normal approximation CI for the true percentage will be calculated taking into account the correlation between bleeding episodes for a given patient in calculating the standard error of the estimate  $\hat{p}$ .

The null and alternative hypotheses for the primary efficacy endpoint are as follows:

$$H_0: p \leq 0.55$$

$$H_1: p > 0.55.$$

The null hypothesis will be tested using a one-sided, one-sample, normal approximation test and a test statistic obtained by dividing ( $\hat{p} - 0.55$ ) by its estimated standard error, taking into account the correlation between bleeding episodes for a given patient. The test will be conducted at the 0.0125 level (adjusted from 0.025 to 0.0125 to account for multiplicity of testing). Treatment of mild/moderate bleeding episodes in the study with LR769 of a given dose will be regarded as successful if it is concluded that the true percentage of successfully treated bleeding episodes with that dose is greater than 0.55. The primary endpoint for the FDA is to satisfy the requirements of the US FDA for the evaluation of success.

No imputation of missing data will be performed for the primary analysis of the primary efficacy endpoint. However, two sensitivity analyses will be performed in order to examine the effect of missing data, if any, on the results of the primary analysis. In the first sensitivity analysis, all bleeding episodes for which the value of the primary efficacy endpoint is missing will be assigned as failures. In the second sensitivity analysis, all such bleeding episodes will be assigned as successes.

In addition, the proportions of successfully treated mild/moderate bleeding episodes will be compared between the two LR769 treatment doses at a 2-sided alpha of 0.05.

Two sensitivity analyses based on Generalized estimating equations (GEE) logistic regression analyses and Generalized linear mixed effects models (GLMM) will be used to assess the robustness of the result by accounting for the within-subjects correlation.

The primary efficacy endpoint for the EMA is defined as the proportion of bleeding episodes (mild/moderate and severe combined) with a “good” or “excellent” patient (for mild/moderate bleeding episodes) and physician (for severe bleeding episodes) reported assessment of efficacy at 12 hours after the first administration of study drug. This proportion of success will be evaluated by the EMA as part of the assessment of the benefit risk ratio for each dosing regimen.

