**Statistical Methods:**

All data collected in this study will be documented using summary tables and patient data listings. Continuous variables will be summarized using descriptive statistics, specifically the sample size (n), mean, median, standard deviation, minimum and maximum. Categorical variables will be summarized by frequencies and percentages.

*Analysis Populations:*

The Enrolled Population will be defined as all patients who signed informed consent. Analyses of non-treatment emergent AEs (non TEAEs) will be done on the Enrolled Population.

The Safety Population will be defined as all patients who received treatment (either in Phase A and/or Phase B). All analyses of safety will be performed based on the Safety Population.

The Treated Population will be defined as all patients who received treatment for at least one bleeding episode, and each such bleeding episode will be analyzed as treated. All analyses of efficacy will be performed based on the Treated Population.

Pharmacokinetic analyses will be performed on the Evaluable PK Population, defined as all treated patients who have a post-injection Factor VIIa activity measurement.

*Sample Size Determination:*

The proportion ( $\hat{p}$ ) of mild/moderate bleeding episodes treated with each dose of LR769 that are classified as being successfully treated will be compared with an objective performance criterion (OPC) of 0.55. A one-sided, one-sample normal approximation test, with an alpha = 0.0125 (adjusted from 0.025 to 0.0125 to account for multiplicity of testing), will be used to test the null hypothesis that  $p \leq 0.55$  versus the alternative hypothesis that  $p > 0.55$ , where p is the true proportion of mild/moderate bleeding episodes that are classified as successes. This will be done for each treatment regimen.

With a true proportion of success of 0.70, a correlation among bleeding episodes for a given patient of 0.1, and an OPC of 0.55, a sample size of 22 patients with a total of 352 mild/moderate bleeding episodes (assuming 8 bleeding episodes per treatment regimen per patient) will provide statistical power  $\geq 80\%$ . The study will enroll at least 24 patients, to account for dropouts and potential unevaluable bleeding episodes.

*Efficacy Evaluation:*

The primary efficacy endpoint for this study is defined as successful treatment of a bleeding

---

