### 3.1.2.2 Treatment of Mild/Moderate Bleeding Episodes

Treatment of a mild/moderate bleeding episode will be initiated as soon as possible but certainly within 4 hours of first symptoms of the bleeding episode. Treatment will consist of

an IV administration of either 75 µg/kg or 225 µg/kg of LR769 as a bolus injection administered in  $\leq$  2 minutes.

During the 75 µg/kg treatment regimen, the initial 75 µg/kg dose may be followed 3 hours later with 75 µg/kg every 3 hours until the bleeding is successfully treated. A maximum of 8 treatments in total are allowed in this treatment regimen for mild/moderate bleeding episodes.

During the 225 µg/kg treatment regimen, the initial 225 µg/kg treatment may be followed 9 hours later with 75 µg/kg every 3 hours until the bleeding episode is successfully treated. A maximum of 6 treatments in total are allowed in this treatment regimen for mild/moderate bleeding episodes.

If the bleeding episode is not successfully treated as assessed as an excellent or good response at 24 hours after the first administration, treatment with LR769 may not be continued and alternative treatment must be considered depending on the remaining symptoms (and be noted as concomitant medication). Treatment of this bleeding episode should not be continued with LR769 (study drug) in that case. The patient's physician may determine the best treatment in that case. This may be another bypassing agent [REDACTED]  
[REDACTED] or other hemostatic treatment.

Patients are allowed to be treated for another bleeding episode in a different anatomical location within 24 hours after initial start of treatment, provided the response to treatment of the initial bleeding episode was either "good" or "excellent". Occurrence of a bleeding episode in the same joint/anatomical location after 24 hours of the last treatment of the initial bleeding episode when an initial "good" or "excellent" response has been achieved will be treated as a new bleeding episode. If the bleeding episode occurs within 24 hours after the last treatment of the initial bleeding episode when an initial "good" or "excellent" response has been achieved, this is regarded a true recurrence and therefore a treatment failure. There is no restriction on the number of bleeding episodes that can be treated with LR769 for each patient in this study. The use of LR769 for prophylaxis is not permitted.

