## 9 PLANNED STATISTICAL METHODS

### 9.1 General Considerations

This section outlines the key components of the planned statistical analyses. Detailed methodology for the statistical analyses will be documented in a Statistical Analysis Plan (SAP). The SAP may modify the plan outlined in the protocol; however, any major modifications will also be reflected in a protocol amendment. If after database lock changes are made to the SAP, these deviations will be documented in the Clinical Study Report (CSR).

All data collected in this study will be documented using summary tables and patient data listings. Continuous variables will be summarized using descriptive statistics, specifically the sample size (n), mean, median, standard deviation, minimum and maximum. Categorical variables will be summarized by frequencies and percentages.

Where applicable, analyses will be done for all patients and by age group (aged from birth to  $<6$  years and  $\geq 6$  years to  $<12$  years).

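### The primary test applies a normal cut-off to a standard error estimated from about 22 patients, so its one-sided level is about 0.016–0.022 instead of 0.0125 unless the main SAP corrects it

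*Protocol*

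**What the plan says.** Section 9.5.1 of the protocol, repeated in the synopsis under Statistical Methods, defines the test that decides success at each dose. "The null hypothesis will be tested using a one-sided, one-sample, normal approximation test and a test statistic obtained by dividing" (p-hat − 0.55) "by its estimated standard error, taking into account the correlation between bleeding episodes for a given patient". On the level it says: "The test will be conducted at the 0.0125 level (adjusted from 0.025 to 0.0125 to account for multiplicity of testing".

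Section 9.2 gives the same normal test and notes: "The standard error used in the denominator of the test statistic will account for the correlation among bleeding episodes for a given patient". It plans on "a sample size of 22 patients with a total of 352 mild/moderate bleeding episodes", that is 8 bleeds per patient per regimen, with a true success proportion of 0.70 and a within-patient correlation of 0.1, and claims at least 80% power. At least 24 patients are to be enrolled, to cover dropouts and unevaluable bleeds.

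Neither section names the SE estimator, says whether the variance is taken at p-hat or at 0.55, or gives a t reference or other small-sample correction. The GEE and GLMM analyses in section 9.5.1 are sensitivity analyses and do not decide success. Section 9.1 leaves detail to the SAP: "Detailed methodology for the statistical analyses will be documented in a Statistical Analysis Plan (SAP". The SAP supplied is an addendum to main SAP version 2.0 of 12 September 2017. The addendum does not define the primary test, and the main SAP was not supplied.

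**The concern.** Bleeds within a patient are correlated, so the independent units for the variance are the patients, about 22, and not the 176 bleeds per regimen. A normal cut-off treats the SE as known. An SE estimated from 22 patients is noisy, and a cut-off that ignores this rejects too often.

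There is a second effect when the variance is estimated from the data. Above 0.5, a high p-hat goes with a small p-hat(1 − p-hat): 0.66 × 0.34 = 0.224, against 0.55 × 0.45 = 0.2475. The SE is therefore smallest when p-hat is high by chance.

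The trial has no control arm, so this comparison with 0.55 carries the confirmatory error control. Alpha was halved so that the chance of declaring at least one ineffective dose successful stays at 0.025. If the real level per dose is nearer 0.02, much of that adjustment is lost.

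**Working it through.** **Inputs (protocol section 9.2):** null value 0.55, true value 0.70, correlation 0.1, K = 22 patients, 8 bleeds per patient per regimen, N = 22 × 8 = 176 per regimen, one-sided alpha 0.0125.

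**The plan's power figure.**
- Design effect: 1 + (8 − 1) × 0.1 = 1.7.
- SE at 0.55: √(0.55 × 0.45 × 1.7 / 176) = 0.0489. SE at 0.70: √(0.70 × 0.30 × 1.7 / 176) = 0.0450.
- Normal cut-off: z(0.9875) = 2.241.
- Power with null variance: Φ((0.15 − 2.241 × 0.0489) / 0.0450) = 0.815.
- Power with variance at 0.70: Φ(0.15 / 0.0450 − 2.241) = 0.862.

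Both meet the stated 80%, so the figure reproduces. It does not reveal which variance is intended.

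**Rough check of the level.** With 21 degrees of freedom, P(t > 2.241) = 0.018. The t cut-off for 0.0125 is 2.414.

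**Estimators.** For patient i with n_i bleeds and y_i successes:
- Cluster SE: V0 = Σ(y_i − n_i p-hat)² / N². CR1 multiplies V0 by K/(K − 1). CR3 with equal counts multiplies it by (K/(K − 1))².
- ANOVA-ICC: p-hat(1 − p-hat)(1 + 7 × estimated correlation)/N, or the same with 0.2475 in place of p-hat(1 − p-hat) (null variance).
- Centred cluster SE: Σ(y_i − 0.55 n_i)² / N².

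**Simulated one-sided level at p = 0.55** (beta-binomial data, equal counts, correlation 0.1, 400,000 trials, Monte Carlo SE about 0.0002):

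| Estimator and reference | 22 × 8 | 24 × 8 |
|---|---|---|
| Uncorrected cluster, z | 0.0223 | 0.0212 |
| CR1, z | 0.0203 | 0.0191 |
| ANOVA-ICC at p-hat, z | 0.0196 | 0.0189 |
| CR3, z | 0.0186 | 0.0175 |
| ANOVA-ICC, null variance, z | 0.0165 | 0.0156 |
| Centred cluster, z | 0.0124 | 0.0121 |
| CR3, t on Satterthwaite df | 0.0129 | 0.0126 |

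A separate simulation with 600,000 replicates gave 0.0168 to 0.0228 with z at 22 patients for estimated, uncentred SEs, and 0.0125 for the centred one. Common-shock data instead of beta-binomial changed these by no more than 0.0002. It also showed that t with 21 df alone is not enough: CR1 with t is still at 0.0150.

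**Two doses.** If the doses were independent, CR1 would give 1 − (1 − 0.0203)² = 0.040. Simulation (300,000 trials) gives the chance of at least one false success, with patient effects shared / independent between regimens:
- CR1, z: 0.037 / 0.040
- All uncentred estimators in the table, z: from 0.031 (null variance, shared) to 0.044 (uncorrected, independent)
- Centred, z: 0.023 / 0.025
- CR3 with Satterthwaite df: 0.024 / 0.026

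**Sensitivity to the assumptions.**
- Correlation 0.05 to 0.3: CR1 with z 0.020–0.022, ANOVA-ICC null variance with z 0.015–0.017, centred with z 0.012–0.014, CR3 with t on 21 df 0.013–0.014.
- Correlation fixed at 0.1 rather than estimated, null variance: level 0.011 if the true correlation is 0.1, but 0.025 if it is 0.2.
- Unequal bleed counts: section 3.1.2.2 says "There is no restriction on the number of bleeding episodes that can be treated with LR769 for each patient in this study", but the documents give no spread. Assuming a total of 176 and a between-patient rate CV of 0 to 0.8, the levels are CR1 with z 0.022–0.030, CR3 with Satterthwaite df 0.013, and centred with z 0.0095–0.012.

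**Power at p = 0.70 (22 × 8, then 24 × 8):** CR1 with z 0.83 and 0.86; CR3 with Satterthwaite df 0.77 and 0.81; centred with z 0.77 and 0.81.

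**The case against.** The strongest objection is that the fault depends on a document not seen. Section 9.1 gives the detail to the SAP, and the SE estimator is the kind of detail main SAP version 2.0 would hold. The estimator decides the result: the centred cluster SE holds the level with z, and no supplied text says that another was planned. This stands as a condition on the finding. It does not remove the point, because the protocol fixes the normal reference and most natural readings of its SE then exceed 0.0125.

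The practical effect is also small. The success margin needed above 0.55 moves from about 0.109 (CR1, z) to about 0.120 (CR3, t), and 0.011 × 176 is about 2 bleeds. With the null-variance ICC estimator the excess is only 0.004 per dose. Every patient is scheduled to cross between regimens, so shared patient effects are plausible, and these give the lower two-dose figures. All of this stands: only borderline results would change.

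The suggested correction is not exact. It gives 0.0129, and 0.0133 to 0.0137 with common-shock data. That is still much closer to 0.0125 than the uncentred estimators with z.

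Finally, unequal counts do not always raise the level: the centred SE becomes conservative. The GEE and GLMM analyses give some check on robustness, but they do not decide success and no small-sample correction is stated for them.

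**Conclusion.** The concern holds for the test as the protocol states it. With 22 patients and 8 bleeds per regimen, correlation 0.1 and a true proportion of 0.55, the usual estimated SEs with a normal cut-off give 0.0165 to 0.022 per dose, an excess of 0.004 to 0.010 over 0.0125. Enrolling 24 patients does not cure it (0.0156 to 0.0212). The sample size calculation itself is sound on its own terms.

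The conclusion assumes that main SAP version 2.0 names neither a null-centred cluster SE nor a small-sample correction. The larger excess under unequal bleed counts rests on an assumed spread. This should be fixed because it concerns the confirmatory error rate, though it would alter only a result close to the boundary.

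**What to change.** 1. In section 9.5.1, the synopsis and the SAP, name the SE estimator and replace the normal cut-off with a small-sample reference. One suitable choice is a CR3-type patient-cluster SE with t on Satterthwaite df (21 with 22 patients and equal counts). Check its level by simulation at the observed bleed counts.
2. Restate the power in section 9.2 and the synopsis for that test. It is 0.77 at 22 × 8, so the stated 80% is not met there. It is 0.81 at 24 × 8 (384 bleeds per 24 × 16 in total), but this uses up the margin that section 9.2 reserves for dropouts and unevaluable bleeds.
3. If main SAP version 2.0 already defines a cluster SE centred on 0.55, write that into section 9.5.1 and the synopsis instead. The normal cut-off then holds the level, and only the power needs restating (0.77 at 22 × 8, 0.81 at 24 × 8).
4. If the database is locked, report the corrected test beside the planned one in the CSR, which is where section 9.1 places SAP changes made after lock.

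No new data are needed. The cost is a lower stated power and, if the sponsor regards the change as a major modification, the protocol amendment that section 9.1 then requires.
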